If no target lesion was present at screening (but documented as a non-target lesion) the response at Week 16 should be documented as follows:

Non-Target Lesions	New Lesions	Overall Response
CR	No	CR
Non-CR/non-PD	No	SD (non-CR/non-PD)
Not measurable/Not assessed	No	NE
PD (Unequivocal)	Yes or no	PD
Any	Yes	PD

The latter case should not occur on MRI assessments since a measurable lesion is required for study entry, but it may occur on clinical breast examination, mammography, and/or breast U/S assessments. An overall response of PR is not possible per RECIST 1.1 if only non-target lesions are documented at screening.

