3.7.2. Analysis for secondary endpoints

The two secondary efficacy endpoint measures in PIK3CA WT population will be summarized by treatment arm and will be analyzed analogous to the primary efficacy endpoints. Information on PIK3CA mutation status (HistoGeneX: variable PIK3CAREsC) is assessed centrally. Patients with early study termination and hence missing efficacy outcome, as well as patients who are NE for MRI by central review will be considered as non-responders in the analysis.

The further endpoint measures will be summarized by treatment arm and will be compared between the two treatment arms within each population based on appropriate statistical analyses: locally assessed ORR will be compared using a Cochran Mantel-Haenszel test, stratified by tumor size and nodal status within each method; change in Ki67, PEPI score and change in enhancing tumor volume will be compared by appropriate regression analysis models (depending on the distribution of the variables), e.g. logistic regression models, adjusted for tumor size and nodal status. For each of the different definitions of pCR, comparisons between treatment arms will be done by Cochran Mantel-Haenszel test, stratified by tumor size and nodal status.

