3.10.1. Exploratory endpoints

ORR (centrally assessed, ICON: dataset RVIS, variable RRESPONS – CR, PR, SD, Non-CR/Non-PD, PD, NE, ND), pCR rate (local, tpCR - yes, no, not assessed), PEPI score (derived – classified into risk groups according to Ellis et al 2008 as PEPIR and PEPIB, respectively) according to the decrease in Ki67 after 2 weeks of treatment are hypothesized to differ between patients receiving letrozole plus GDC-0032 compared to patients receiving letrozole plus placebo. Each will be evaluated in all randomized patients and, if statistically significant within all randomized patients, also in PIK3CA MT patients.

The concordance of the different imaging modalities in measuring tumor response after completion of study drug (MRI, central, ICON: dataset RVIS, variable RRESPONS – CR, PR, SD, Non-CR/Non-PD, PD, NE, ND; clinical, ultrasound and mammography, local, OverResp for each - CR, PR, SD, PD, not measurable/not assessed) will be observed. Concordance will be evaluated in all randomized patients.

Rates of planned BCS (local, SurgTypePlan - breast conserving, other levels) and conversion to BCS (local, SurgType - breast conserving, other levels) between patients receiving letrozole plus GDC-0032 and patients receiving letrozole plus placebo will be compared. Rates will be evaluated in all randomized patients.

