3.10.2. Analysis for exploratory endpoints

Comparisons between treatment arms in ORR (grouped as responder vs. non-responder), pCR rate and PEPI score according to the decrease in Ki67 will be analyzed using appropriate regression analysis models (depending on the distribution of the variables), e.g. logistic regression models, adjusting for tumor size and nodal status in all randomized population and in PIK3CA MT population. Concordance will be examined by frequencies and percentages. Rates will be summarized descriptively.

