Lymph nodes merit special mention since they are normal anatomical structures that may be visible by imaging even if not involved by tumor. Axillary lymph nodes are known to vary widely in size, and signs of abnormality in axillary lymph nodes on imaging include other morphological findings often in addition to changes in nodal size. For these reasons, pathologic axillary lymph nodes on imaging should be identified as non-target lesions at baseline. Change in short-axis dimension may be considered in the assessment of pathology, but measurements are not required, and these lesions should be followed qualitatively, as described below at each response assessment time point.

Signs of lymph node pathology on imaging include the following:

- Increase in short axis dimension
- Thickened cortex, either diffusely or asymmetrically enlarged
- Thinning, or replaced fatty hilum
- Irregular margins or spiculations

- Rim enhancement
- Decreased echogenicity of cortex
- Perinodal edema

EVALUATION OF RESPONSE

Evaluation of Target Lesions

This section provides the definitions of the criteria used to determine objective tumor response for target breast lesions:

- Complete response (CR): disappearance of all target lesions
- Partial response (PR): at least a 30% decrease in the sum of diameters of target lesions, taking as reference the baseline sum of diameters
- Progressive disease (PD): at least a 20% increase in the sum of diameters of target lesions, taking as reference the smallest sum on study (nadir), including baseline

In addition to the relative increase of 20%, the sum must also demonstrate an absolute increase of at least 5 mm.

The appearance of one or more new lesions is also considered progression.

- Stable disease (SD): neither sufficient shrinkage to qualify for PR nor sufficient increase to qualify for PD, taking as reference the smallest sum on study

Special Notes on the Assessment of Target Lesions

Target Lesions That Become Too Small to Measure. While on study, all lesions recorded at baseline should have their actual measurements recorded at each subsequent evaluation, even when very small (e.g., 2 mm). However, sometimes lesions that are recorded as target lesions at baseline become so faint on imaging that the radiologist may not feel comfortable assigning an exact measure and may report them as being too small to measure. When this occurs, it is important that a value be recorded on the CRF as follows:

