- If it is the opinion of the radiologist that the lesion has likely disappeared, the measurement should be recorded as 0 mm.
- If the lesion is believed to be present and is faintly seen but too small to accurately measure, BML (below measurable limit) should be indicated.

To reiterate, however, if the radiologist is able to provide an actual measure, that should be recorded, and, in that case, BML should not be ticked.

Lesions That Split or Coalesce on Treatment. When non-nodal lesions fragment, the longest diameters of the fragmented portions should be added together to calculate the target lesion sum. Similarly, as lesions coalesce, a plane between them may be maintained that would aid in obtaining maximal diameter measurements of each individual lesion. If the lesions have truly coalesced such that they are no longer separable, the vector of the longest diameter for the coalesced lesion should be recorded.

Evaluation of Non-Target Lesions

This section provides the definitions of the criteria used to determine the tumor response for any non-target lesions identified at baseline. Although some non-target lesions may actually

be measurable, they need not be measured and, instead, should be assessed only qualitatively at the timepoints specified in the protocol.

- CR: disappearance of all non-target lesions
 - All lymph nodes must be non-pathologic in appearance
- Non-CR/Non-PD: persistence of one or more non-target lesion(s)
- PD: unequivocal progression of existing non-target lesions. For pathologic axillary lymph nodes, this may be based on a combination of morphological factors, including a potential increase in short-axis dimension

Special Notes on Assessment of Progression of Non-Target Disease

To achieve unequivocal progression on the basis of the non-target disease, there must be an overall level of substantial worsening in non-target disease in a magnitude that, even in the presence of SD or PR in target disease, the overall tumor burden has increased sufficiently to merit discontinuation of therapy. A modest increase in the size of one or more non-target lesions is usually not sufficient to qualify for unequivocal progression status. The designation of overall progression solely on the basis of change in non-target disease in the face of SD or PR of target disease will therefore be extremely rare.

New Lesions

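### Patients with only non-target disease on palpation, mammography or ultrasound can never be scored PR there, yet they stay unflagged in local ORR and in the concordance with MRI

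*SAP*

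**What the plan says.** Section 3.1.4 judges response for each modality against that modality's own screening assessment. If no target lesion was recorded on a modality at screening, only CR, SD (non-CR/non-PD), NE or PD is available: "An overall response of PR is not possible per RECIST 1.1 if only non-target lesions are documented at screening". The section says this should not happen on MRI, because entry requires a measurable MRI lesion, but that "it may occur on clinical breast examination, mammography, and/or breast U/S assessments".

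Appendix 1 explains why. PR requires "at least a 30% decrease in the sum of diameters of target lesions", and of non-target lesions it says that "they need not be measured and, instead, should be assessed only qualitatively at the timepoints specified in the protocol".

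Section 3.7.1 evaluates local ORR in all randomized patients and by PIK3CA status. Section 3.7.2 then says that "locally assessed ORR will be compared using a Cochran Mantel-Haenszel test, stratified by tumor size and nodal status within each method". For the imaging modalities, section 3.10.1 says "Concordance will be evaluated in all randomized patients" and section 3.10.2 says "Concordance will be examined by frequencies and percentages". Neither section excludes, flags or separately tabulates patients without a target lesion on the modality concerned.

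**The concern.** The exploratory objective in section 2.1.5 is concordance of the modalities in measuring tumour response. Take a tumour that halves on both MRI and mammography, but was recorded at screening as a target lesion on MRI and only as a non-target lesion on mammography. MRI gives PR and mammography gives SD. The mismatch is settled at screening and says nothing about whether the two methods saw the same change. A low percentage agreement could then mean either that a method tracks response poorly or that it often had no measurable lesion to start from, and the planned output cannot separate the two.

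In the secondary local ORR, the same patients can count as responders only if all disease on that modality disappears. They lower the rate in both arms and shrink the difference. The amount may vary between the three methods, because the share of patients affected may vary.

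**Working it through.** **Do other rules in the SAP remove these patients?**
- Section 3.1.2.1 limits analyses to evaluable measurements. SD is an evaluable result, so they stay in.
- The local variables have a level for not measurable or not assessed. In the section 3.1.4 table that row leads to NE. Non-target disease that was assessed and persists leads to SD.
- The levels listed for the central MRI variable include Non-CR/Non-PD (sections 3.7.1 and 3.10.1). Those listed for the local variables do not. The level exists where the case should not occur and is absent where it may, so locally these patients merge with true SD.

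**Inputs**
- Share *f* of patients with only non-target disease on a modality: not in the SAP. Assumed 2%, 10% or 20%.
- MRI PR rate in these patients: not in the SAP. Assumed 40% to 50%.
- ORR 40% versus 64%: the planning rates in section 2.4 for MRI ORR in the PIK3CA MT cohort. Used here only to illustrate local ORR.

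**The plan's own figure.** Section 2.4 gives no figure on this point, but the borrowed rates are consistent with its sample size. With 40% versus 64%, two-sided alpha 16%, 80% power, 40:60 allocation (control the smaller arm) and continuity correction, 43 + 64.5 = 107.5 patients are needed, against the stated 108.

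**Forced disagreement.** At category level an MRI PR cannot be matched, so forced disagreement = *f* × MRI PR rate.

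**Diluted local ORR.** If these patients respond at the same rate *q* in both arms, observed ORR = (1 − *f*) × *p* + *f* × *q*. The *f* × *q* term cancels between arms, so the difference = (1 − *f*) × 24 points. The rates below take *q* = 0.

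| *f* | Forced disagreement (points) | Local ORR, control vs GDC-0032 | Difference (points) |
|---|---|---|---|
| 2% | 0.02 × 40 to 0.02 × 50 = 0.8 to 1.0 | 39.2% vs 62.7% | 0.98 × 24 = 23.5 |
| 10% | 0.10 × 40 to 0.10 × 50 = 4 to 5 | 36.0% vs 57.6% | 0.90 × 24 = 21.6 |
| 20% | 0.20 × 40 to 0.20 × 50 = 8 to 10 | 32.0% vs 51.2% | 0.80 × 24 = 19.2 |

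**Sensitivity to *q*.** If these patients do carry a treatment effect through complete responses, with a share *c* of responders being CR, the difference is (1 − *f* + *f* × *c*) × 24. For *f* = 20% and *c* = 20% this is 0.84 × 24 = 20.2 points.

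**Power, for scale.** An unstratified 5% two-sided comparison of 40% with 64% at 54 per arm (108 / 2) has 71.0% power. With *q* = 0 this becomes 61.7% at *f* = 10% and 52.6% at *f* = 20%.

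**The case against.** The scoring rule is deliberate and disclosed: section 3.1.4 tabulates it, names the modalities and attributes it to RECIST 1.1. Without measured diameters a 30% decrease cannot be shown. A reader might infer that the rule is an error; the documents do not support that. The gap lies only in how sections 3.7 and 3.10 use its output.

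A reader might also infer that the all-randomized concordance gives a wrong answer. That is too strong. If mammography cannot measure a lesion that MRI can, its failure to register PR is arguably real discordance. Concordance given measurability on both modalities is a different question, and restricting to it can make a weak modality look better. This stands, and it is why the restricted analysis belongs beside the planned one and not in its place.

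The frequency may be low. Section 3.1.4 says the case may occur, not that it will be common. Section 2.2 requires primary tumours of at least 2 cm and separately recognises primaries not evaluable by ultrasound at baseline, so some poorly seen lesions may be NE and not SD. This also stands, and 2% is shown for that reason. The forced-disagreement figure assumes MRI PR is as frequent in these patients as assumed overall. It also counts some disagreement that ordinary measurement differences would have produced anyway.

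The consequence has limits too. Complete disappearance still scores CR, so not every shrinking tumour becomes SD. If concordance is read as responder versus non-responder, an MRI PR paired with a local CR agrees.

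**Conclusion.** The point holds as a minor one. Sections 3.1.4, 3.7 and 3.10 together let patients who cannot be scored PR on a local modality enter that modality's ORR and its concordance with MRI, with nothing in the planned output to identify them.

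For 2% to 20% affected, forced disagreement runs from about 1 to 10 percentage points, and an illustrative 24-point difference in local ORR falls to between about 23.5 and 19.2 points. These sizes rest on the assumed share, an assumed 40-50% MRI PR rate, MRI planning rates for the PIK3CA MT cohort carried over to local ORR, and no treatment difference among the affected patients.

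A reader might infer a biased treatment comparison or a threat to the primary result. Neither follows. Measurability at screening precedes treatment and randomization should balance it, so the effect is dilution, conservative for the comparison, and not a false benefit. Co-primary MRI ORR requires a measurable MRI lesion and is untouched. Local ORR is secondary; concordance is exploratory and descriptive.

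**What to change.** Keep the all-randomized analyses and add the following.

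- **Section 3.10:** for each pair of modalities, concordance in patients with a target lesion at screening on both and an evaluable Week 16 response on both.
- **Section 3.7.2:** for each local method, the same stratified comparison in patients with a target lesion at screening on that method. Target lesions are identified at screening, so this subset is fixed before treatment and keeps the randomised comparison.
- **Reporting:** the number of patients per method and arm without a target lesion at screening, with local Non-CR/Non-PD shown separately from SD.

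The cost is SAP wording and a few extra tables. Section 3.1.4 already requires lesions to be documented at every assessment, so no new data collection should be needed. The restricted tables have smaller denominators: out of 330 patients, about 323, 297 or 264 per local method at 2%, 10% or 20% affected, before losses from non-evaluable Week 16 assessments.

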3.1.5. Statistical considerations

Cochran-Mantel-Haenszel (CMH) tests will be used for several comparisons (e.g. ORR, pCR) between treatment arms, stratified by tumor size and nodal status. No clear rule regarding the requirements for using stratified CMH test based on the combined cell frequencies over all strata could be found in literature (compare Glenn A. Walker 2004: Common Statistical Methods for Clinical Research, 2nd Edition, p 316). Hence, the CMH test will be used only if there is at least 1 responder in each stratum and the number in each cell of the unstratified 2x2 table is greater than 5. Otherwise, unstratified Fisher’s Exact test will be used.

3.2. Types and timepoints of analyses

3.2.1. Main analyses

The main analysis used for preparing the Top Line Results (TLR) will be done after all patients underwent their post-surgery visit or dropped out of the study early and after clinical database closure and data management review.

The following data were not captured in the clinical database, but were assessed and/or gathered by external vendors:

- Response by centrally assessed MRI
- PIK3CA mutation status
- Data on KI67, ER status (Allred score) and expression of biomarkers
- PTEN (phosphatase tensin homolog)

- MRI volume
- ECG data

External vendor data available, received and checked by ABCSG prior to clinical database closure will be examined for the main analysis. After clinical database closure unblinding will occur at ABCSG with randomization information received from the IxRS vendor.

ABCSG will receive additional information regarding the concentration of GDC-0032 and letrozole for the pharmacokinetic, pharmacogenetic and biomarker endpoints after unblinding. The final analysis will be performed after all external vendor data are available, received and checked by ABCSG.

3.2.2. Independent Data Monitoring Committee analyses

The Independent Data Monitoring Committee (IDMC) will conduct an interim analysis to review the unblinded safety data after the first 20 patients have either 1) finished the 30-day, follow-up visit after the surgery, or 2) been on study for 20 weeks after the randomization date (for those who do not receive the surgery), whichever occurs first. All available information of all randomized (i.e. enrolled) patients with all available assessments at the respective time point will be included in the interim analyses.

In addition, the IDMC will monitor accumulating patient safety data at a minimum of once every 6 months until the last patient has completed study treatment. Additional details (e.g., IDMC members, communication, affiliations) will be provided in the IDMC charter and the details of the scope of analysis for IDMC will be documented separately. Furthermore, the IDMC or the Medical Monitor may request additional ad hoc meetings of the IDMC at any time during the study to review safety data.

3.3. Analysis populations

3.3.1. Intention-to-Treat population

Primary and secondary analyses, as well as patient-reported and exploratory analyses, will include the Intention-to-Treat (ITT) population; that is, all patients who were randomized regardless of whether they received any study drug (GDC-0032 or placebo). Patients will be analyzed according to the treatment group to which they were assigned at randomization.

3.3.2. Per-protocol population

Sensitivity analyses will be based on the Per-Protocol (PP) population; that is, all patients who were randomized, received study drug (GDC-0032 or placebo), received more than 90% and less than 110% of the per protocol intake of GDC-0032 and who do not have any protocol violations that mandate their exclusion from the PP population. Hence, patients with Important Protocol Deviations (IPDs) that are expected to impact the primary endpoint of the study will be excluded (compare Study GO28888 (LORELEI)_Note-to-File_02-Feb-2016-

Signed.pdf): [ipd-DO01], [ipd-IN04n], [ipd-PE02n], [ipd-EX01], [ipd-EX02], [ipd-EX05], [ipd-EX06], [ipd-EX07], [ipd-EX12], [ipd-EX13], [ipd-EX20] and [ipd-EX26]. Patients will be analyzed according to the treatment actually received. Hence, randomized patients who wrongly received active drug at any time point will be included in the experimental arm in the PP population.

3.3.3. Safety population

Safety analyses will be based on the safety (SAF) population and include all randomized and treated patients (patients who received at least one dose of study treatment). Patients will be analyzed according to the treatment actually received. Hence, randomized patients who wrongly received active drug at any time point will be included in the experimental arm in the SAF population.

3.4. Significance level

A two-sided significance level of 16% and 4% is used for the co-primary endpoints MRI ORR and pCR, respectively, resulting in an overall, two-sided, family-wise type I error rate for the primary endpoints of 20% for each analysis population (all randomized and PIK3CA MT patients). All other tests will be performed at a two-sided significance level of 5%.

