2.4. Number of subjects - sample size estimation

This study is designed for testing the effect of GDC-0032 on the two co-primary endpoints in all enrolled patients and in the PIK3CA MT patients and plans to enroll 330 patients in total. Assuming the PIK3CA mutation status will not be available (unknown) for approximately 10% of the patients and the prevalence of PIK3CA MT is 40%, there will be approximately 120 patients in the PIK3CA MT cohort.

Given that the PIK3CA mutation status is not a stratification factor for randomization, there might be a possible imbalance between treatment arms within the PIK3CA MT cohort, which may reduce the statistical power in this cohort. To ensure the study provides sufficient statistical power even when the treatment assignment is imbalanced, the sample size was calculated based on a conservative scenario by assuming that the treatment assignment imbalance in PIK3CA MT is 40% vs. 60%. The sample size was calculated based on a χ^2 -test using continuity correction (Ury and Fleiss 1980).

To control an overall, two-sided, family-wise error rate under 20% for each analysis population, we use a two-sided significance level of 16% and 4% for the co-primary endpoints MRI ORR, and pCR, respectively.

Assuming 10% of the patients are unevaluable for the MRI ORR, approximately 300 enrolled patients and 108 patients in the PIK3CA MT cohort will be evaluable for analyses. This sample size allows us to detect an absolute percentage increase of 24% in MRI ORR rate in the letrozole plus GDC-0032 arm (64%) versus the letrozole plus placebo arm (40%; Smith et al. 2005; Ellis and Ma 2007) in the PIK3CA MT cohort at 80% power and 16% two-sided significance level. The minimal detectable difference for ORR is approximately 15%.

Assuming that all patients are evaluable for pCR (i.e., approximately 330 enrolled patients and 120 in the PIK3CA MT cohort), this sample size provides 80% power to detect an absolute percentage increase of 18% in pCR in the letrozole plus GDC-0032 arm (19%) versus the letrozole-only arm (1%, Smith et al. 2005; Ellis and Ma 2007) in the PIK3CA MT cohort at the 4% two-sided significance level. The minimal detectable difference for pCR rate is approximately 13%.

The study is considered positive if at least one population shows a statistically significant result regarding the co-primary endpoints.

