3.6.2. Analysis for primary endpoints

The efficacy endpoint tumor ORR will be calculated by treatment arm in all randomized population and in PIK3CA MT population. Within each population, summary tables will be given and the ORR for the two treatment arms will be compared at a two-sided alpha of 16% using a Cochran Mantel-Haenszel test, stratified by tumor size and nodal status. The efficacy endpoint pCR rate will also be calculated and compared at a two-sided alpha of 4% based on the same analytical approach as ORR. The two alpha values account for a family-wise type I error rate of 20% for each population (all randomized patients and PIK3CA MT patients).

Patients with early study termination and hence missing efficacy outcome (ORR or pCR), as well as patients who are NE for MRI by central review (ORR only) will be included and considered as non-responders in the analysis.

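### The fixed 16%/4% split controls the 20% error rate as stated, but it passes no alpha on; weighted Holm would add power for the second co-primary claim at no cost in patients

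*SAP*

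**What the plan says.** Three sections of the SAP give the same levels. Section 3.4: "A two-sided significance level of 16% and 4% is used for the co-primary endpoints MRI ORR and pCR, respectively". Section 2.4 gives the purpose: "To control an overall, two-sided, family-wise error rate under 20% for each analysis population". Section 3.6.2 repeats it: "The two alpha values account for a family-wise type I error rate of 20% for each population".

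Neither level depends on the other endpoint's result. On pCR, section 3.6.2 says: "The efficacy endpoint pCR rate will also be calculated and compared at a two-sided alpha of 4% based on the same analytical approach as ORR". No Holm, fallback, hierarchical or graphical step appears in the SAP. The success rule in section 2.4 is: "The study is considered positive if at least one population shows a statistically significant result regarding the co-primary endpoints". The two endpoints therefore work as alternatives, each with its own share of the error.

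**The concern.** When two endpoints share an error budget and one of them succeeds, its share can be passed to the other without raising the family-wise error. The SAP does not do this. If ORR is significant at 16%, pCR is still held to 4%, although a 20% test would stay within the stated budget. In the other direction, ORR stays at 16% after a pCR success.

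What is at stake is the power to claim the second endpoint, mainly pCR, whose level could rise from 4% to 20%. ORR would move only from 16% to 20%.

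**Working it through.** **Inputs (SAP 2.4, 3.4, 3.6.2).** Alpha is 0.16 for ORR and 0.04 for pCR. In the mutant cohort, ORR is 40% vs 64% with N = 108 and pCR is 1% vs 19% with N = 120. Allocation is 40:60, and sizing uses a chi-square test with continuity correction. The SAP gives no correlation between the endpoints, so 0 to 0.5 is assumed.

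**1. Error rate of the plan.** The bound is 0.16 + 0.04 = 0.20. Under the global null with independent endpoints it is 1 − 0.84 × 0.96 = 0.194; at correlation 0.5 it is about 0.183. The stated 20% holds.

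**2. The plan's own power.** Power = Φ[(d − z·s0)/s1]. Here d is the difference less 0.5(1/n1 + 1/n2), s0 is the pooled standard error and s1 the unpooled one. The smaller arm is taken as control.
- ORR (43.2/64.8): d = 0.24 − 0.0193 = 0.2207, and (0.2207 − 1.405 × 0.0978)/0.0955 = 0.87, so power is 80.8%.
- pCR (48/72): d = 0.18 − 0.0174 = 0.1626, and (0.1626 − 2.054 × 0.0601)/0.0484 = 0.81, so power is 79.1%.

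Both reproduce the stated 80%. At the 20% level the same formula gives 84.1% for ORR and 96.1% for pCR.

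**3. Weighted Holm, same weights.** The first step is the same pair of tests (16% and 4%). If either is significant, the other is tested at 20%. The chance of at least one claim and the global-null error are therefore unchanged. If only one null is true, that endpoint is tested at no more than 20%. Control at 20% thus holds under any dependence. With independent endpoints:
- pCR: 0.7908 + 0.8085 × (0.9615 − 0.7908) = 0.929
- ORR: 0.8085 + 0.7908 × (0.8411 − 0.8085) = 0.834
- Both, fixed split: 0.8085 × 0.7908 = 0.639
- Both, Holm: 0.8085 × 0.9615 + 0.7908 × (0.8411 − 0.8085) = 0.803

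| Correlation | pCR | ORR | Both |
|---|---|---|---|
| 0 | 79.1% → 92.9% | 80.8% → 83.4% | 63.9% → 80.3% |
| 0.3 | 79.1% → 91.1% | 80.8% → 83.2% | 66.5% → 80.9% |
| 0.5 | 79.1% → 89.7% | 80.8% → 83.0% | 68.6% → 81.4% |

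**4. Check with the tests likely to be used.** Section 3.1.5 sends sparse tables to Fisher's exact test. At a 1% control rate, 48 controls yield 0.48 expected responders, so Fisher would apply to pCR. Simulation with an unstratified chi-square for ORR (40% vs 64%, all 120 patients) and Fisher for pCR, with pCR either nested in response or independent of it, gives for pCR power:

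| Control/active | 1% vs 19% | 1% vs 12% |
|---|---|---|
| 48/72 | 90% → 97-98% | about 48% → 82% |
| 60/60 | 92% → 97-98% | 57% → 80% |
| 72/48 | 95% → 98% | 71% → 86% |

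The SAP does not say which arm is the smaller, so both directions are shown. Power for both endpoints at the plan's rates goes from 80-81% to 90% with 48/72, and from about 85% to 90% with 72/48. Section 3.6.2 counts patients unevaluable on MRI as non-responders. If the plan's ORR rates refer to evaluable patients and 10% are unevaluable, they become 0.9 × 40% = 36% and 0.9 × 64% = 57.6%. Power for both is then about 76% → 85% with 48/72.

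In all randomized patients (165/165, assumed ORR 40% vs 55% and pCR 1% vs 5%), pCR power rises from 45% to 70%.

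**5. The price.** With ORR effective and pCR truly equal, the permitted false pCR claim rises from 4% to at most 20%. With Fisher and a 48/72 split, the simulated rate under Holm is about 4% at a common pCR rate of 1%, and about 11% at 5%. It is lower with 60/60.

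**The case against.** The strongest reply is that nothing here is wrong. The three sections agree, the split delivers its 20%, and the sizing reproduces. The success rule gains nothing, because the chance of at least one claim is identical under both procedures. All of this stands and makes the point an efficiency suggestion.

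The stricter level for pCR may also be deliberate. A sponsor can accept 20% for any claim and still not want a pCR claim at p near 0.20. For example, 0/48 vs 4/72 (Fisher p = 0.149) would count as a pCR success once ORR was significant. That is weak evidence. This objection stands as a reason to keep 4%, but the SAP does not give it: the only purpose stated for the levels is family-wise control.

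A reader might infer that a true pCR effect below the planned 18 points would usually be missed under the fixed split. The figures do not support that. Fisher power at 4% for 1% vs 15% is still 71% (48/72), 77% (60/60) and 85% (72/48). It falls below 50% only at about 12% or less in the least favourable mutant-cohort allocation, or near 5% in all randomized patients.

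The size of the gain depends on test, allocation and correlation. At an assumed 1% vs 10% with 48/72, the continuity-corrected method gives 29% → 58-59% and Fisher 30% → 72%. With 72/48, Fisher gives 56-57% → 77%. The direction does not depend on these choices.

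**Conclusion.** The split is a valid weighted Bonferroni procedure that leaves power unused. Weighted Holm with the same weights does at least as well in every outcome, at the same 20% within each population. At the plan's mutant-cohort rates the gain is about 11-14 points for pCR, 2-3 points for ORR, and 13-16 points for both endpoints by the plan's continuity-corrected method. With chi-square and Fisher, the gain for both endpoints is about 5-10 points. These sizes rest on the assumed correlation, the assumed arm sizes and unstratified tests; the dominance itself rests on none of them.

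Two stronger readings are not supported. The SAP does not breach its stated error rate, and the plan does not lose probability of a positive study. Nor does Holm settle the error across the two overlapping populations. The 20% is defined per population while success in either counts, and that is a separate matter.

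Priority: optional, a cheap improvement.

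**What to change.** In section 3.4, with matching wording in 2.4 and 3.6.2, state: Within each population, ORR is tested at 16% and pCR at 4%; if either is significant, the other is tested at 20% (weighted Holm). The condition for a positive study stays as it is.

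If the sponsor wants a stricter bar for pCR, keep 4% and add one sentence giving that as the reason.

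The change needs no patients and no new data. It must be fixed before unblinding, and matched in the protocol if the split is also stated there. Section 4 of the SAP lists no departure from the protocol on alpha, so it probably is. The addendum in section 5 already reports analyses prompted by unexpected results. The rule cannot be applied retroactively to results already seen; after unblinding it could only be reported as a post hoc analysis.
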